8. STATISTICAL METHODS AND STATISTICAL ANALYSIS

8.1. Statistical Methods

8.1.1. Analysis of continuous data

Summary statistics (number of patients, mean, standard deviation, median, maximum, minimum) will be calculated.

8.1.2. Analysis of categorical data

The frequency (e.g., number of patients) and proportion of each category will be calculated in the tabulation at each evaluation time point.

For the evaluation of a change from baseline in the number of patients at each evaluation time point after the start of treatment, the number and proportion of patients (the number of patients in each category at baseline is used as the denominator) will be calculated using a cross table.

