### 8.3.7. Confirmation of survival

The survival status until the end date of observation period in each booklet (or until the first visit date after discontinuation of this drug) should be recorded. In the case of death, the date of death and cause of death [ cardiovascular event, or others (including unknown) ] should be recorded.

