7. HANDLING OF MISSING DATA

If treatment with this drug is continued even after the end of the observation period and the end date of treatment is missing, the end date of observation will be handled as the end date of treatment in this study.

If the seriousness, causal relationship, and action taken and outcome regarding adverse events are missing, these data will be handled as “unknown” for tabulation.

For the efficacy endpoints and laboratory test values, if there is no measurement within the time window for each evaluation time point (Appendix 1), data will be handled as missing, and the missing data will not be complemented.

The strategy for handling data with uncompleted cleaning is described below:

- Items of missing data: The items will be handled as missing (category of categorical variables is “unknown”) for both tabulation and listing.
- Items of inconsistent data: The items will be handled as missing for both tabulation and listing. However, a list of data handling should be prepared separately.
- No signature: Any entry in a case report form without the signature of the contracted physician (including a case report form with the signature of an uncontracted physician only) will be handled as missing for both tabulation and listing. If there is no date of signature in the field for the date of signature or if there is inconsistency in the date entered (e.g., date before the start date of treatment, future date), the entry in the case report form will be regarded as having no signature.

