8.2.4.1. NYHA functional classification

The NYHA functional classification at each evaluation time point [at baseline, Month 12, Month 30, discontinuation] will be summarized as described in Section 8.1.2.

The NYHA functional classification at each evaluation time point after the start of treatment [at Month 12, Month 30, discontinuation] will be summarized using a cross table as described in Section 8.1.2.

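### The by-visit NYHA table states no denominator and neither NYHA table shows deaths, so a falling class III/IV share could reflect mortality rather than improvement

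*SAP*

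**What the plan says.** SAP 8.2.4.1 plans two NYHA summaries.

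- **By-visit table.** "The NYHA functional classification at each evaluation time point [at baseline, Month 12, Month 30, discontinuation] will be summarized as described in Section 8.1.2". The rule it points to in SAP 8.1.2 reads: "The frequency (e.g., number of patients) and proportion of each category will be calculated in the tabulation at each evaluation time point". No denominator is given. The NYHA categories in SAP 5.4 and 8.2.2.1 are classes I to IV, with no level for death.
- **Cross table.** "The NYHA functional classification at each evaluation time point after the start of treatment" (Month 12, Month 30, discontinuation) is also cross-tabulated against baseline. Here SAP 8.1.2 does fix the denominator: "the number of patients in each category at baseline is used as the denominator".

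On missing values, SAP 7 says that when an efficacy endpoint has no measurement in its time window, "data will be handled as missing, and the missing data will not be complemented". A separate list in SAP 7, for data whose cleaning is incomplete, says "Items of missing data: The items will be handled as missing", with an unknown category for categorical variables. Neither rule mentions death.

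Protocol 8.3.7 has sites record "The survival status until the end date of observation period in each booklet", or up to the first visit after the drug is stopped, with date and cause of death. Under Protocol 8.2.6 and SAP 2.1, observation of a patient who stops the drug ends at that first visit. SAP 8.2.4.3 counts all-cause and cardiovascular deaths over the whole observation period, and SAP 8.2.4.4 adds Kaplan-Meier survival stratified by the SAP 5.4 factors, which include NYHA class.

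**The concern.** Change in NYHA class is one of three efficacy endpoints (SAP 6.2) in a cohort without a control group (Protocol 8.9). The displayed class distribution is therefore itself the result. A patient who dies before a visit window has no NYHA value for that window, and the SAP does not say where that patient goes in either table.

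If the by-visit proportions are taken over assessed patients, and patients in class III/IV die more often than those in I/II, the remaining patients are a healthier mix. The table then drifts towards I/II even if nobody's class changes, and a reader could take the drift for stabilisation or improvement. In the cross table the gap is different: part of each row is unaccounted for, and the reader cannot tell how much of it is death.

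**Working it through.** **Inputs.** The documents give neither a baseline NYHA mix nor mortality by class, so the plan has no figure on this point to reproduce and every rate below is assumed. A cohort of 300 (the target in Protocol 8.5.1) is used only to show counts. Two simplifications apply: no survivor changes class, and death is the only reason for a missing value.

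**By-visit table, assessed patients as denominator.** Let p be the baseline share in III/IV, and let d1 and d2 be the proportions dead by Month 30 in III/IV and in I/II. Then

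III/IV share at follow-up = p(1 − d1) / [p(1 − d1) + (1 − p)(1 − d2)].

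With p = 0.30, d1 = 0.40 and d2 = 0.15: 0.30 × 0.60 = 0.18; 0.70 × 0.85 = 0.595; 0.18 / 0.775 = 23.2%. The share falls from 30% to 23% with nobody improving. Overall mortality in this example is 1 − 0.775 = 22.5%.

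Over a range of assumptions, the III/IV share among assessed patients becomes:

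| Baseline III/IV | Deaths 20% in III/IV, 5% in I/II | 40%, 10% | 50%, 15% | 30%, 30% |
|---|---|---|---|---|
| 20.0% (60/300) | 17.4% | 14.3% | 12.8% | 20.0% |
| 33.0% (99/300) | 29.3% | 24.7% | 22.5% | 33.0% |
| 50.0% (150/300) | 45.7% | 40.0% | 37.0% | 50.0% |

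The last column shows that the shift comes only from unequal mortality.

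**Same patients, all 300 as denominator, death shown.** Take 99/300 in III/IV with deaths of 40% and 10%. Survivors are 99 × 0.60 = 59.4 in III/IV and 201 × 0.90 = 180.9 in I/II (expected counts).

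- I/II: 180.9 / 300 = 60.3%.
- III/IV: 59.4 / 300 = 19.8%.
- Dead: 59.7 / 300 = 19.9%.

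III/IV or dead is 39.7%, up from 33.0% in III/IV at baseline. With assessed patients only, the same data show III/IV falling to 59.4 / 240.3 = 24.7%.

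**Cross table.** Take 100 patients in III/IV at baseline, of whom 10 improve and 20, 40 or 50 die.

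- Baseline denominator, as the SAP states: improved = 10/100 = 10.0% in all three cases. The row is short by 20%, 40% or 50%.
- Assessed-only denominator, which the SAP does not state: 10/80 = 12.5%, 10/60 = 16.7%, 10/50 = 20.0%.

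The stated rule therefore protects the improvement proportion. It leaves the shortfall unexplained.

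**The case against.** A reader might infer that NYHA class is reported only in survivors, that deaths are hidden, and that improvement will be overstated throughout. The documents do not support that, for three reasons.

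- **The cross table covers the same follow-up time points.** In the 30% example its III/IV row would show 0% moving to I/II, 60% still in III/IV and 40% absent, so no false improvement appears. This stands. Only by reading the baseline count as limited to patients with a follow-up value would the problem return, and that is not the plain reading.
- **Assessed patients as the by-visit denominator is an inference.** The SAP is silent, and SAP 7 has an unknown category. This stands too: the defect is an unstated denominator, not a wrong one. But the unknown category is listed for data with incomplete cleaning, and even if used here it would merge deaths with lost records.
- **Deaths are reported.** SAP 8.2.4.3 tabulates them, and SAP 8.2.4.4 stratifies survival by NYHA class. This stands against any claim of concealment, but it does not fill the gap in the NYHA tables. The death counts run over the whole period. SAP 8.1.4 specifies median, quartiles and plots, with no survival figure at Month 12 or Month 30. SAP 8.2.4.4 also makes reporting of its exploratory analyses conditional on their giving an important interpretation. The end-point status list in Protocol 8.3.6 has no entry for death, so the table of discontinuation reasons (SAP 8.2.1.2) need not isolate it.

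It is also fair to say that the main objective is long-term safety, that SAP 4 treats any test as exploratory, and that NYHA has no death level, so ranking death as its worst class would be a choice. Showing deaths in a separate column requires no such ranking.

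**Conclusion.** The point holds as a minor one. The by-visit NYHA table has no stated denominator, and neither table distinguishes death from other reasons for having no value. If assessed patients are the denominator, higher mortality in III/IV lowers the III/IV share without any survivor improving. Under the assumed rates, that means 20% falling to 13–17%, 33% to 23–29%, or 50% to 37–46%; with equal mortality the shift is zero. These sizes illustrate direction and scale and are not predictions for this cohort.

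The cross table does not overstate improvement; its weakness is a shortfall that cannot be broken down. No sample size, error rate or decision rule is affected, only how a descriptive efficacy table will be read.

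**What to change.** In SAP 8.2.4.1, for Month 12 and Month 30, use efficacy-set patients with a baseline NYHA class as the denominator in both tables. Assign each patient without a NYHA value in the window to exactly one category, in this order:

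1. died during observation by that time point;
2. observation ended early while last known alive (discontinued, transferred or lost to follow-up);
3. under observation, not assessed.

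Each row of the cross table, and each visit in the by-visit table, then sums to 100%. The SAP should also say whether the time point means the nominal month or the end of the window in Appendix 1. The discontinuation time point can stay as planned.

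The cost is a small derivation step, using survival status, date of death and end-of-observation status that are already collected. The order is needed because death and discontinuation can overlap. One limit remains: observation stops at the first visit after discontinuation, so later deaths are not captured and those patients stay in category 2. A footnote to both tables should say so.

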8.1.3. Analysis of binary data

The frequency and its proportion will be calculated. When the confidence interval of the proportion is calculated, the two-sided 95% confidence interval (exact method) will be calculated.

When the proportion is compared between subgroups, the risk ratio and its 95% confidence interval (Wald method) will be calculated.

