5.4. Subgroups

Subgroup analyses of safety will be performed for the following patient characteristics and other factors. For the patient characteristics and other factors with those of specific categories underlined, a risk ratio will be calculated using each underlined category as the reference.

- Inpatient/outpatient status at the first prescription [inpatient, outpatient]
- *Severity of liver impairment [absent, mild, moderate, severe]
- Liver impairment [absent, present]
- Renal impairment [absent, present]
- Age [<15 years, ≥15 to <65 years, ≥65 years]
- *TTR genetic variant [wild-type, variant]
- NYHA functional classification [Class I/II, III/IV]
- NYHA functional classification [Class I, II, III, IV]
- Concomitant medication [absent, present]
- Non-drug therapy (device therapy) [absent, present]

- Complication [absent, present]
- Gender [male, female]
- Usage experience of this drug (administered this drug for the first time, transferred from clinical trials, transition from the treatment of ATTR-PN)

*Evaluation of the important missing information (safety in patients with severe liver impairment and patients with variants)

Subgroup analyses of efficacy will be performed for the following patient characteristics:

- TTR genetic variant [wild-type, variant]
- NYHA functional classification [Class I/II, III/IV]
- NYHA functional classification [Class I, II, III, IV]

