8.2.3.3. Exploratory analysis

For each of the factors specified in Section 5.4, the number and proportion of patients with at least one adverse reaction (incidence of any type of adverse reactions) will be tabulated, and for the incidence, the risk ratio among subgroups for each factor will be calculated as described in Section 8.1.3. However, after reconsidering the classification of a category with <10 patients, if calculation of a risk ratio is difficult, the

risk ratio to the category will not be calculated. In addition, unknown data will be excluded from the evaluation of risk ratios.

Serious adverse reactions and serious adverse events will also be analyzed in the same manner as above.

Adverse reactions will be tabulated by SOC and PT for each of the following subgroups:

- Liver impairment [absent, present]
- Renal impairment [absent, present]
- Age [<15 years, ≥15 to <65 years, ≥65 years]
- Pregnancy status [absent, present]
- NYHA functional classification [Class I, II, III, IV]

The onset status of adverse reactions will be evaluated for each product (Vyndaqel or Vynmac) during the treatment period until the first switching to Vynmac for Vyndaqel and during the treatment period after the first switching to Vynmac for Vynmac.

This drug is contraindicated to patients with a history of hypersensitivity to any of its ingredients. Because of limitations in evaluation in this study, no tabulation regarding contraindications will be performed. However, if hypersensitivity to any of its ingredients is reported as an adverse reaction, it will be presented in a listing.

Additional analyses may be performed as necessary. The exploratory analysis will be reported only when results giving important interpretation are obtained.

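### The Wald interval for subgroup risk ratios does not exist when a group has no events, and the SAP's omission rule depends on patient numbers rather than events

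*SAP*

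**What the plan says.** SAP 8.1.3 treats the two kinds of binary summary differently. For a single proportion, when an interval is given, "the two-sided 95% confidence interval (exact method) will be calculated". For a comparison between subgroups, "the risk ratio and its 95% confidence interval (Wald method) will be calculated". It gives no continuity correction and no rule for zero events.

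SAP 5.4 lists the safety subgroup factors and says that "a risk ratio will be calculated using each underlined category as the reference". Severity of liver impairment and TTR variant are marked there as the evaluation of the important missing information.

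SAP 8.2.3.3 applies this to the incidence of any adverse reaction and adds: "Serious adverse reactions and serious adverse events will also be analyzed in the same manner as above". Its only safeguard has this trigger: "after reconsidering the classification of a category with <10 patients, if calculation of a risk ratio is difficult". When the trigger is met, the ratio for that category is omitted. It does not define when calculation counts as difficult and does not mention zero events. Separately from the ratio, "the number and proportion of patients with at least one adverse reaction (incidence of any type of adverse reactions) will be tabulated" for each factor.

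SAP 4 makes any test result exploratory.

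**The concern.** A Wald interval for a risk ratio needs at least one event in each group. The safeguard looks at the number of patients, but the calculation fails on the number of events. A category of 15 patients with no event is outside the safeguard, and the prescribed interval still cannot be produced. The analyst must then leave it out or choose a method after seeing the data.

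This is most likely where the answer is wanted most: serious adverse reactions, which cannot be more frequent than all adverse reactions, and the missing-information groups (severe liver impairment, variants), which may be small. For a category with no events, the useful output is the largest relative risk still compatible with the data, and the plan as written gives none.

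**Working it through.** **The plan's own figure.** The only computable probability in the documents is in protocol 8.5.2: about 98% for at least 10 hepatotoxicity cases among 300 patients at 5.88%. The exact binomial tail is 98.4%, so it reproduces. The documents state no figure for the risk ratios.

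**Inputs.** The total of 300 patients is from protocol 8.5.1. The documents give no subgroup sizes and no incidence for any adverse reaction, serious adverse reactions or serious adverse events. Category size n1 and incidence p are therefore assumptions, shown as a range. The true ratio is 1 and the reference has n0 = 300 − n1 patients.

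**Why the interval fails.** With a events of n1 in the category and b events of n0 in the reference, the log-scale Wald standard error is √(1/a − 1/n1 + 1/b − 1/n0). The SAP does not name the scale; log is assumed.
- For 1/15 v 17/285 the ratio is 1.12 and the standard error is √(1 − 0.0667 + 0.0588 − 0.0035) = 0.994. The interval is 0.16 to 7.85.
- For 0/15 the term 1/a is 1/0 and there is no interval. The ratio itself is still calculable, as 0.
- Only a zero-event reference leaves the ratio itself undefined.

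**How often.** P(no event in the category) = (1 − p)^n1. The chance of no event in a reference of 285 is at most 0.3% over this range. For n1 = 15, 0.98^15 = 0.739, 0.95^15 = 0.463, 0.90^15 = 0.206 and 0.80^15 = 0.035.

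**What happens if zero-event categories are left out.** Full enumeration of the two binomials gives the mean ratio with zeros kept as 0. Dividing it by 1 − (1 − p)^n1 gives the mean when they are dropped. At 5%: 1.078 / 0.537 = 2.01.

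| p (n1 = 15) | Interval undefined | Mean ratio, zeros kept | Mean ratio, zeros dropped |
|---|---|---|---|
| 2% | 74% | 1.25 | 4.80 |
| 5% | 46% | 1.08 | 2.01 |
| 10% | 21% | 1.03 | 1.30 |
| 20% | 4% | 1.02 | 1.05 |

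The direction reverses when the sparse group is the reference and zero-event references are dropped. At 5.88% the mean ratio is 0.51 with 10 reference patients and 0.86 with 20; with 30 it is back above 1, at 1.09.

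**What a score interval gives at zero events.** The upper limit is the ratio r at which (0 − r·b/n0) / √(p̃1(1 − p̃1)/n1 + r²·p̃0(1 − p̃0)/n0) = −1.96. Here p̃0 and p̃1 = r·p̃0 are the estimates restricted to ratio r.
- 0/15 v 14/285 (4.9% in the reference): at r = 4.33, p̃0 = 0.0389 and p̃1 = 0.1685. The numerator is −0.213 and the root is 0.1086, a quotient of −1.96. The upper limit is **4.33**.
- 0/15 v 29/285 (10.2%): the upper limit is **2.05**.

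**Falsely high intervals, on one basis.** This is the share of all datasets at 5% in which the interval lies wholly above 1. An undefined Wald interval counts as not above 1.

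| n1 | Wald | Score |
|---|---|---|
| 10 | 5.8% | 5.8% |
| 15 | 3.9% | 4.5% |

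In these cases neither method ever lies wholly below 1.

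**The case against.** A reader might infer that zero-event ratios are simply dropped, so that small-subgroup ratios appear only when an event occurred and are biased upwards. The documents do not support this. The omission rule in SAP 8.2.3.3 concerns categories below 10 patients, and applies only after reclassification and only if calculation is difficult. At 10 or more patients the SAP is silent, and a ratio of 0 can be calculated. The averages of 2.0 and 1.3 come from the assumed dropping, not from the Wald method: with zeros kept the mean is near 1 whichever interval is used. The direction also depends on which group is sparse, and the underlining that marks the reference categories cannot be seen in the text available here.

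A reader might also infer that the score interval covers much better. At 5% and 10 patients, Wald coverage is 86% against 94% for the score interval. But the first figure is conditional on the Wald interval being calculable, while the second is over all datasets. On a common basis the falsely high rates are about the same, as shown above.

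Three further points stand:
- Reassuring zeros are not hidden. Counts and proportions are tabulated for every factor in 5.4, and SAP 9 lists adverse reactions in patients with variants and with severe liver impairment.
- The analyses are exploratory.
- Appendix 2, the worked risk-ratio example, is not readable here, so a zero-event convention may exist there.

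None of this supplies the missing interval. A count of 0/15, or a ratio of 0 alone, does not say how large a relative risk remains possible.

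**Conclusion.** The point holds in a limited form. The interval named in SAP 8.1.3 cannot be produced when a group has no events, and the safeguard in 8.2.3.3 is tied to the wrong quantity and to an undefined term. For a non-reference category of 15, the interval is missing in between 4% (20% incidence) and 74% (2% incidence) of datasets. These figures rest on assumed sizes and rates, a true ratio of 1, 300 patients in total and a log-scale Wald interval. The loss is the upper limit for zero-event categories. Upward bias would follow only if those categories were left out, which is an inference. Under that assumption it is material for small categories and rare outcomes, and slight at 20% incidence. This is a worthwhile clarification, not a threat to the study's conclusions.

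**What to change.** - In SAP 8.1.3, replace the Wald method for the risk ratio with a score interval (Koopman or Miettinen-Nurminen).
- Report a non-reference category with no events as ratio 0 with its upper limit.
- In SAP 8.2.3.3, replace the undefined difficulty criterion: omit the ratio only when the reference group has no events, and show counts with exact confidence intervals there.
- If Appendix 2 already holds a zero-event convention, state it in 8.1.3 and make the two agree.

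Adding 0.5 to zero cells is not an adequate substitute. It gives a finite interval (0/10 v 17/290: 0.76, 0.05 to 11.8), but under no effect the mean ratio is still 1.50 at 10 patients and 5.88%.

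The cost is one option in standard software and a few sentences in the SAP, with no new data. The downside is wide intervals in sparse categories.

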8.1.4. Analysis of period data (time to event onset)

The median, first quartile, and third quartile will be calculated by the Kaplan-Meier method. For period data which includes interval-censored data, the median, first quartile, and third quartile will be calculated based on the EMICM algorithm. In addition, Kaplan-Meier plots will be prepared.

8.1.5. Analysis of longitudinal data measured repeatedly

When longitudinal data is analyzed using a mixed model repeated measure (MMRM), parameters will be estimated using the restricted maximum likelihood estimation method (REML), and an unstructured variance-covariance structure will be assumed for within-subject variation. If the model fails to converge, a different available optimization method will be tried. If the problem of convergence is still not resolved, estimation will be performed by changing the assumption of variance-covariance structure in the order of TOEPH, ARH(1), AR(1), and CS. The model-adjusted mean change from baseline at each evaluation time point will be summarized using the least squares mean and its 95% confidence interval.

When individual data are graphically presented, the time-courses of all measured values will be presented using line graphs.

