### 7.1. Safety specifications

Important Potential Risks: Hepatotoxicity, hypersensitivity reactions, reproductive and developmental toxicity, infection, incorrect product selection between Vyndaqel and Vynmac

Important Missing Information: Safety in patients with severe hepatic impairment, administration to patients with variants

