8.2.4.2. Cardiac biomarkers

For NT-pro BNP, BNP, troponin I, and troponin T each, the following analyses will be performed:

Measurements of each biomarker at each evaluation time point [at baseline, Month 6, Month 12, Month 18, Month 24, Month 30, discontinuation] will be summarized as described in Section 8.1.1. In addition, a

change from baseline in each biomarker at each evaluation time point [at Month 12, Month 30, discontinuation] will be summarized as described in Section 8.1.1.

A change from baseline in each biomarker at each evaluation time point will be summarized, as described in Section 8.1.5, using an MMRM with patient as a random effect; TTR genetic variant [wild-type, variant], NYHA functional classification [I/II, III/IV], and evaluation time point [Month 6, Month 12, Month 18, Month 24, Month 30] as fixed effects; and baseline value as a covariate. The analysis will be performed on values measured on the nearest day to each time point for the evaluation using the model.

Evaluation time points may be changed depending on the status of data accumulation.

In addition, measured values at all time points in each patient will be used to prepare spaghetti plots for the entire observation period, as described in Section 8.1.5. (Figures using different colors [or separated by line type] will be prepared for both TTR genetic variant [wild-type, variant] and NYHA functional classification [I, II, III, IV].)

Preparation of an MMRM and figures will not be included in the subgroup analysis.

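### The adjusted biomarker change is reported as a least squares mean with no weights stated; the usual equal weighting would pull it away from the surveyed case mix and widen its interval if that mix is uneven

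*SAP*

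**What the plan says.** SAP 8.1.5 sets the summary measure for the repeated-measures model: "The model-adjusted mean change from baseline at each evaluation time point will be summarized using the least squares mean and its 95% confidence interval". It fits an unstructured covariance and, if that does not converge, falls back "in the order of TOEPH, ARH(1), AR(1), and CS". SAP 8.2.4.2 gives the fixed effects as "TTR genetic variant [wild-type, variant], NYHA functional classification [I/II, III/IV], and evaluation time point" (Months 6, 12, 18, 24 and 30), with "baseline value as a covariate". It lists no interaction between a factor and time. Neither section states weights for the factor levels.

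The same section plans descriptive summaries of the measured values at every time point, but of change from baseline only "at Month 12, Month 30, discontinuation] will be summarized as described in Section 8.1.1". SAP 8.1.1 defines those summaries as number of patients, mean, standard deviation, median, maximum and minimum, with no confidence interval. The model itself is not repeated by subgroup: "Preparation of an MMRM and figures will not be included in the subgroup analysis".

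Protocol 8.9 records that there is no control group. The documents give no expected split by TTR type or NYHA class. Variants appear only as missing information in Protocol 7.1 ("administration to patients with variants"), and NYHA class as a subgroup factor in SAP 5.4 ("NYHA functional classification [Class I/II, III/IV").

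**The concern.** In a randomised comparison with an additive model, the weights given to covariate levels cancel out of the treatment difference. Here each adjusted mean is itself the result, so the weights matter. Under the usual default, the variant group supplies half of the TTR average and NYHA III/IV half of the NYHA average, whatever their shares among treated patients.

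Protocol 8.7 wants the time course of the biomarkers from the start of treatment, and the approval conditions call for a survey of all patients. A mean at the surveyed mix answers that question. An equal-weight mean answers it only if both splits are near even or the factors have no effect. Otherwise the estimate leans towards the smaller groups, and their sampling error widens the interval. With the weights unstated, two programmers could both follow the SAP and report different adjusted means from the same data.

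**Working it through.** The plan states no precision figure for this model, so there is none to reproduce. Its only probability statement, about 98% for at least 10 hepatotoxicity cases in 300 patients at 5.88%, does reproduce (exact binomial 0.984) but has no bearing here.

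**Inputs.** From the SAP: two binary factors, five visits, baseline as covariate, no factor-by-time interaction. Assumed, because the documents do not give them: the shares p (variant) and q (NYHA III/IV), independence of the two factors, within-patient correlation, and dropout.

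**Step 1: shift.** Write the change at visit t as m_t + b1 × (variant) + b2 × (III/IV) + g × (baseline − mean baseline).
- Equal-weight mean: m_t + 0.5 b1 + 0.5 b2
- Observed-margin mean: m_t + p b1 + q b2
- Difference: (0.5 − p) b1 + (0.5 − q) b2

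Without factor-by-time terms this is the same at every visit, and a larger sample does not reduce it. Its direction and size depend on b1 and b2, which the documents do not give.

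**Step 2: standard error at a single visit.** The variance ratio, equal weights over observed margins, is 1 + (0.5 − p)²/[p(1 − p)] + (0.5 − q)²/[q(1 − q)].
- p = 10%, q = 25%: 1 + 0.16/0.09 + 0.0625/0.1875 = 3.11; SE ratio 1.76
- p = 20%, q = 35%: 1 + 0.09/0.16 + 0.0225/0.2275 = 1.66; SE ratio 1.29
- p = 5%, q = 25%: 1 + 0.2025/0.0475 + 0.0625/0.1875 = 5.60; SE ratio 2.37

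**Step 3: standard error in the planned five-visit model.** The factor effects are common to all visits, so they are estimated from all visits together and the ratios fall. By generalised least squares, the variance of an adjusted mean is L′(ΣXᵢ′Vᵢ⁻¹Xᵢ)⁻¹L. L holds the visit indicator and either (0.5, 0.5) or (p, q) for the two factors, with baseline at its mean in both. The ranges below cover autoregressive and exchangeable correlation from 0.4 to 0.8, with retention complete or falling to 60% by Month 30.

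| Variant p | III/IV q | Shift | SE ratio, single visit | SE ratio, five visits |
|---|---|---|---|---|
| 50% | 50% | 0 | 1.00 | 1.00 |
| 20% | 35% | 0.30 b1 + 0.15 b2 | 1.29 | 1.09 to 1.25 |
| 10% | 25% | 0.40 b1 + 0.25 b2 | 1.76 | 1.25 to 1.68 |
| 5% | 25% | 0.45 b1 + 0.25 b2 | 2.37 | 1.50 to 2.23 |

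Heavier dropout (one fifth of patients left at Month 30, autoregressive correlation 0.6) lowers the Month 30 ratio to 1.17 or 1.18 at 10% variant with 30% or 20% III/IV, and to 1.06 at 20% and 30%.

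**Step 4: what the other outputs cover.** Unadjusted change is planned at Month 12, Month 30 and discontinuation. At Months 6, 18 and 24 the model gives the only planned summary of change, and it gives the only confidence interval for change at any visit.

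**The case against.** The strongest reply is that the SAP never prescribes 50:50. It says least squares mean and nothing more, and observed-margin means would also comply. That stands: equal weighting is the convention that applies when nothing else is said, so the gap is that the weights are not stated.

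A reader might also infer that the plan will describe a population that was not surveyed. The documents do not support that as a fact. They give no TTR or NYHA split, and near an even split the difference vanishes. The shift also needs the change to differ between levels, and no such difference is documented.

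A third tempting inference is that 300 patients would yield the precision of about 96 (300/3.11 at 10% variant and 25% III/IV). That uses the single-visit formula, which does not fit the five-visit model. In addition, 300 is the target for the safety analysis set, not the number of patients contributing to a biomarker model. The figure should not be used.

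It is fair, too, that the treated population's course is partly visible elsewhere: descriptive values at every time point, unadjusted change at three, the same summaries by TTR type and NYHA class (SAP 8.2.4.4 with 5.4), and individual plots distinguished by both factors. These soften the point but do not remove it, for the reasons in Step 4. Adjusted and raw means can differ under any weighting, because the model adjusts for baseline and uses incomplete patients, so disagreement alone is not a fault.

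Finally, observed margins are not free of choices. Counted over data rows, they would overweight patients with more visits. They will also vary somewhat between biomarkers and between the full and consented sets. The first problem is met by counting each patient once; the second is a small real cost.

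**Conclusion.** The point holds as an unstated choice whose usual default suits this survey poorly. If the case mix is uneven, an equal-weight mean departs from the surveyed mix by the Step 1 expression and carries a wider interval than needed. The SE ratio is about 1.1 to 1.3 at 20% variant and 35% III/IV, about 1.2 to 1.7 at 10% and 25%, and 1 at 50:50. These sizes rest on assumed shares, independent factors, an additive model, and assumed correlation and dropout; only the algebra follows from the SAP. The consequence is limited, since SAP 4 treats all testing as exploratory, no decision rule depends on this estimate, and unadjusted changes are also reported at three time points. It is still worth correcting, because the remedy is cheap and the adjusted mean is the only planned result for change at three of the five visits.

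**What to change.** Add to SAP 8.1.5, with a cross-reference in 8.2.4.2, that adjusted means are computed at the observed proportions of TTR type and NYHA class, counted once per patient in the model's analysis set, and at the mean baseline value. Equal-weight means may be shown as a sensitivity analysis.

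The cost is a sentence in the SAP and a small change to the program, which must take the proportions from one record per patient and not from the visit-level data. The one downside is that the reference mix will differ slightly between the four biomarkers and between the full and consented sets. If a single reference is preferred, fix one common set of margins and name it in the SAP.
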